7.0 Enrollment

Goal enrollment is 168 participants.

Potential subjects will be identified via chart review on admission to the stroke service and appropriateness of enrollment will be decided by PI based on discussion with the patient's clinical care team. The patient will then be approached on the inpatient stroke service, provided information about the study by a study team member at bedside and have time to ask questions before consent is obtained by a study team member. The PI/study team will already be part of these patients' clinical care and the PT or nurse practitioner obtaining consent will be an approved member of the study team on the eIRB application.

Inclusion/exclusion criteria will be determined based on patient chart review in Epic, once PT consults are received (consults are automatically triggered on admission to the acute stroke service). Thorough chart review and discussion with patient's medical team will serve as a means of determining patient eligibility. Both treatments as usual and experimental group patients will meet the same eligibility criteria and will be randomized to their treatment after consent is obtained.

Inclusion Criteria:

Acute stroke

NIH Stroke Scale score of 2-18 with motor involvement

Age 18-80yo

Medical stability for increased therapy services, determined by Stroke Service NP (no significant uncontrolled fluctuation in vital signs, blood pressures or seizure like activity).

Ability to give informed consent

Oriented x 4 and able to follow commands

Exclusion Criteria:

Medical instability or cerebral perfusion dependence, requiring bed rest

Pregnancy (noted in chart)

Inmates (noted in chart or visible by guards present at bedside)

Known & Current COVID-19 infection (PCR positive labs)

Dialysis (noted in chart & performed while inpatient)

External Carotid Stenting Procedure

Hemorrhagic Stroke

8.0 Informed Consent

To conduct this research, we will require a signed informed consent from all patients. Consent will be obtained by PI, Co-I and study personnel. The PI/study team will already be part of these patients' clinical care and the PT or nurse practitioner obtaining consent will be an approved member of the study team on the eIRB application. The signed informed consent is necessary to be randomized to one of four study groups. A written copy of the consent form will be provided to the patient by a study member at bedside, on the inpatient stroke service. The participant will be given the opportunity to read the consent, their questions will be answered, and they will be provided with a copy of the consent document. Capacity to consent will be determined by the patient's primary medical team. For patients who are unable to physically sign their name (secondary to weakness or hemiparesis from stroke), they may use make a mark on the consent and there will be a witness to the consent process.

9.0 Study Design

This study will be designed as a randomized control trial with a 1:1:1:1 randomization. This study will utilize a stratified block randomization design and stratifying on the 4 NIHSS categories to randomly allocate a participate to a treatment group, while maintaining a balance across treatment groups. All patients will be identified and consented as soon as possible, ideally within 24 hours of admission to the stroke service. Patient's blood pressures will be obtained prior to PT treatment to ensure safety of mobilization. If systolic blood pressure is above 220mmHG, therapy services will not be performed at that time and therapist will follow up later in the day once patient is medicated for hypertension by nursing staff.

If a patient is randomized to the frequent physical therapy treatment group, they will receive PT services 2x/day for 3 out of the first 5 days of hospital admission and daily for the remainder of their hospitalization. Sessions will be 20-50 minutes in duration, based on patient tolerance. These PT sessions will include working on getting out of bed, transferring from bed to a chair, working on balance, strengthening the side of the body affected by the stroke, learning how to walk again and/or how to use a wheelchair if unable to walk.

If a patient is randomized to the intense physical therapy treatment group, they will receive PT services daily with treatment sessions being more difficult than a standard therapy session. During each PT session, the things that are difficult for the patient will be made even more difficult (by adding resistance or other challenges) in order to increase the intensity of the session. This is known as "Error Augmentation training" and will be implemented to target at least 3 post stroke deficits identified on evaluation.

If a patient is randomized to the frequent AND intense physical therapy treatment group they will receive PT services 2x/day for 3 out of the first 5 days of hospital admission and daily for the remainder of the hospitalization. Sessions will be 20-50 minutes in duration (based on patient tolerance) and will focus on increasing the intensity of services by making difficult tasks more difficult with the addition of resistance or other challenges. This is known as “Error Augmentation training” and will be implemented to target at least 3 post stroke deficits identified on evaluation. If a patient is randomized to the standard of care group they will receive the normal amount of PT services one a day, three to five days week for 20-50minutes throughout admission. The patient will be assisted to perform transfers and mobility tasks with a PT providing facilitation to assist the patient without the component of an added challenge.

Functional measures such as PASS, AMPAC, mRS will be collected on initial PT evaluation, day three of treatment and discharge from the acute care hospital. These measures will be collected again in the outpatient neurology clinic (or virtually via Zoom or Doxy.me) at 30 day follow up appointment. Study procedures will end after 30 day follow up appointment is completed.

Participants can ask to end PT sessions early if they become uncomfortable or do not want to do them.

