1.0 Objectives and Specific Aims

Goal: *To evaluate the impact of increased frequency and intensity of Physical Therapy (PT) services on patient outcomes in the acute stroke population.*

Aim I: To determine whether increasing the frequency of Physical Therapy services post-acute stroke is superior to standard of care physical therapy services; measured by a change in functional outcomes, hospital length of stay, 30 day follow up.

Hypothesis I: We hypothesize that patients receiving an increased frequency of PT services will demonstrate higher degree of improvement on the Activity Measure for Post-Acute Care (AMPAC) and Postural Assessment Stroke Scale (PASS) from admission to time of discharge from the hospital and at 30-day follow up. We also expect lower overall Modified Rankin Scale (mRS) scores for the increased frequency PT group compared the usual care PT group at 30 days post stroke.

Aim II: To determine whether increasing the intensity of Physical Therapy services post-acute stroke is superior to standard of care physical therapy services; measured by a change in functional outcomes, hospital length of stay, 30 day follow up.

Hypothesis II: We hypothesize that patients receiving an increased intensity of PT services will demonstrate higher degree of improvement on the AMPAC and PASS from admission to time of discharge from the hospital and at 30-day follow up. We also expect lower overall mRS scores for the increased frequency PT group compared the usual care PT group at 30 days post stroke.

Aim III: To determine whether increasing the intensity of Physical Therapy (PT) services post-acute stroke is superior to increasing the frequency of PT services; measured by a change in functional outcomes, hospital length of stay, 30 day follow up.

Hypothesis III: We hypothesize that patients receiving an increased intensity of PT services will demonstrate higher degree of improvement on the AMPAC and PASS from admission to time of discharge from the hospital and at 30-day follow up. We also expect lower overall mRS scores for the increased intensity PT group compared the increased frequency PT group at 30 days post stroke.

Aim IV: To determine whether increasing the intensity and frequency of PT services post-acute stroke is superior to increasing only the intensity of PT services; measured by a change in functional outcomes, hospital length of stay, 30 day follow up.

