2.0 Background

The Department of Physical Therapy in conjunction with the Comprehensive Stroke Center at the Medical University of South Carolina (MUSC) seeks support for developing an evidence-based approach for the mobilization of patients within the first 24 hours of admission for an acute stroke and for increasing the frequency and intensity of acute PT services while inpatient. This evidence will prepare physical therapists and guide practice in the delivery of acute stroke mobilization in the hospital setting to optimize length of stay, disposition planning, and enhance long term recovery outcomes.

Our research hopes to challenge the clinical paradigm regarding the possibility of decreased functional outcomes with early mobilization post stroke. We acknowledge that acute stroke patients may not be able to tolerate an extensive early mobility program but may benefit from shorter more frequent sessions of therapy early in their recovery. Throughout the literature, there are clinical practice guidelines for both the inpatient rehabilitation and outpatient therapy sectors and post stroke recovery. Little is known about the contribution of therapy services in the acute hospital setting and therapy's impact on long term functional gains. The goal of this project is to determine the appropriate dosage of post stroke mobility in the acute care hospital setting.

The objective is to determine if changing one component of the overall mobility dosage, adjusting frequency or intensity, will improve patient outcomes. Phase I of this study, performed at MUSC from June 2021-June 2022, demonstrated improved functional mobility outcomes at hospital discharge for patients who received a combination of both increased frequency and intensity of PT services compared to the standard of care approach. Phase II aims to determine if these promising results can be attributed to increased frequency, increased intensity or a combination of frequent and intense PT sessions. As a comprehensive stroke center, MUSC strives to provide the best of patient care by committing to a higher standard of clinical service utilizing evidence-based practice to improve patient outcomes.

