We propose to enroll 168 individuals with acute stroke admitted to MUSC and randomize them into increased frequency, increased intensity, increased frequency and intensity combined and usual care PT treatment groups. This study will be designed as a randomized control trial. Patients who agree to participate, will be assigned (at random) to either a treatment arm which will receive either more frequent therapy services, more intense therapy services (increased intensity by incorporating error augmentation training), a combination of frequent and intense therapy services (frequent bouts of error augmentation training) or to the control group (treatment as usual) which will receive the standard amount of therapy services currently provided in the hospital setting (~3-5 times per week). Error augmentation training is an approach that targets what is difficult for the patient and makes it even more difficult, increasing errors to enhance adaptation. By studying the balance, walking and success of patients in the treatment groups compared with the standard of care group- we hope to better understand the contribution of intense PT services, frequency PT services, or a combination of intense and frequent PT services on a patient's independence post stroke. We know from phase I of this study that patients provided with a combination of increased frequency and intensity of PT services demonstrated significant functional improvements (measured by PASS and AMPAC) at

time of hospital discharge and a decreased length of hospital stay when compared to the standard of care PT group. Phase II will help us determine if these promising results can be best attributed to the intensity and error augmentation training portion of PT services, to the frequency of PT services, or to a combination of both frequent and intense PT services post stroke in the acute hospital setting.

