12.0 Outcomes and Analysis

Goal enrollment is 168 participants. Based on the past literature, in similar populations the standard deviation of PASS measurements is at the most 7.20.⁵ Using this, with a sample of 42 patients in each group, with 95% confidence at the end of the study we can estimate this difference within a margin of error of 2.8.

The primary outcome measure will be the change in postural assessment stroke scale scores from time of PT evaluation to hospital discharge. A factorial design will allow for a test of intensity (vs control) and duration (vs control) through pooling across treatment arms. Using the table below, margins (A+C, B+D, A+B, C+D) need to each be 104 given a mean difference of 2.8, standard deviation of 7.2, 80% power and 5% type I error. Given that this is an early phase study, we can increase the type I error to 10% which would decrease the overall sample size needed to 168 patients (42 per arm) whilst still maintaining 80% power.

	Low Intensity	High Intensity	Totals
Low Duration	A	B	A+B
High Duration	C	D	C+D
Totals	A+C	B+D	A+B+C+D

We are planning to conduct the analysis using intention to treat paradigm. In a preliminary analysis we will compute all summary statistics. Initial plots, such as spaghetti plots, will be used to guide our analyses. A general linear mixed model approach will be used to analyze all the outcomes. This model will account for the correlations between time points using either a compound symmetric or spatial structure for the covariance matrix. Post-hoc analyses using Tukey type adjustments will be performed to obtain least squares estimates of the differences between the two randomized groups. Although the study is powered based on only the primary

outcome (PASS), we will apply multiple comparisons adjustments for the rest of the outcomes, using Bonferroni corrections. We will test for the assumptions using diagnostic procedures and take appropriate actions if needed. Also, we will define an outcome to be ‘favorable’ or ‘unfavorable’ based on a threshold and apply generalized linear mixed models with logistic link and repeat the analyses. We will attempt to minimize drop-outs but in case of missing data, we will assume Missing at Random or Missing Completely at Random. If necessary, we will perform multiple imputations. For all analyses, we will use SAS, (MIXED, GLIMMIX, MI and MIANALYZE).

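### The intensity-only arm is scheduled daily and usual care three to five days a week, yet the factorial analysis treats both as the same low level of frequency

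*Combined protocol and SAP*

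**What the plan says.** Label the arms by the cells of the Section 12.0 table: A usual care, B intensity only, C frequency only, D both.

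- **A** (Section 9.0): "normal amount of PT services one a day, three to five days week for 20-50minutes throughout admission".
- **B** (Section 9.0): "they will receive PT services daily with treatment sessions being more difficult than a standard therapy session". No session length or number of days per week is given.
- **C** (Section 9.0): "2x/day for 3 out of the first 5 days of hospital admission and daily for the remainder of their hospitalization". **D** has the same schedule.

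Section 12.0 puts A and B together in the Low Duration row (the text elsewhere calls this factor frequency) and states: "A factorial design will allow for a test of intensity (vs control) and duration (vs control) through pooling across treatment arms". The sample size rests on those pooled groups: "margins (A+C, B+D, A+B, C+D) need to each be 104 given a mean difference of 2.8".

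The intended difference between B and A is stated in three places. Section 2.0: "The objective is to determine if changing one component of the overall mobility dosage, adjusting frequency or intensity, will improve patient outcomes". Section 4.0 defines the intensity arm as "more intense therapy services (increased intensity by incorporating error augmentation training". Aim IV in Section 1.0 asks whether "increasing the intensity and frequency of PT services post-acute stroke is superior to increasing only the intensity of PT services", so B is meant to change intensity and nothing else.

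**The concern.** The trial exists to say whether the Phase I benefit came from intensity, from frequency or from both. That requires A and B to differ only in error augmentation. As written they also differ in how often therapy is given. *Daily* is also the word used for the later phase of the two frequent arms, so on the plain reading B receives part of the frequency intervention while being analysed as low frequency.

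The error would affect both pooled contrasts, in opposite directions: intensity would look better than it is and frequency worse. Randomisation does not protect against this, because the difference is built into the arms, and a larger sample would not remove it. No section reconciles the schedules or adjusts for sessions delivered, and the data list in Section 10.0 does not include sessions or minutes. The size of the problem might therefore not be recoverable afterwards.

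**Working it through.** **1. The plan's own figure.** Inputs from Section 12.0: difference 2.8, SD 7.2, 80% power. Two-sided normal approximation (sidedness is not stated), n per margin = 2(z_α + z_β)² × 7.2² / 2.8².

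- 5% type I error: 103.8, so 104 per margin, as stated.
- 10%: 81.8, so 82 per margin or 164 in total. The plan has 168, which is 84 per margin. Power at 84 is 80.9%.

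The sample size reproduces. The problem is what the margins estimate.

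**2. Bias in the margins.** Let I be the effect of intensity, F the effect of the C/D schedule over usual care, and e the effect of B's extra sessions over A. With additive effects the cell means relative to A are A = 0, B = I + e, C = F, D = F + I. With 1:1:1:1 allocation:

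- Intensity margin = [(B + D) − (A + C)]/2 = I + e/2
- Frequency margin = [(C + D) − (A + B)]/2 = F − e/2
- B − A (Aim II) = I + e

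C and D share one schedule, so D − C = I, with no contribution from e.

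**3. Illustration of size.** The documents give neither e nor a length of stay. Assumptions: 7-day stay; A receives 3 to 5 sessions; C and D receive one session on each of the two early days that are not twice-daily; no intensity effect (I = 0); 2.8 points arise linearly from the extra sessions in C over A. Then k = 2.8/(C − A) points per session and e = k(B − A).

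SE of a margin = 7.2 × √(2/84) = 1.111. Two-sided 10% test, |z| > 1.645.

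C and D sessions: 3×2 + 2 + 2 = 10 if *daily* is seven days, and 3×2 + 2 = 8 if it is five weekdays.

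| Daily means | A | B | C, D | k | e | Intensity bias e/2 | Null intensity rejected | Frequency margin | Power |
|---|---|---|---|---|---|---|---|---|---|
| 7 days | 3 | 7 | 10 | 0.400 | 1.60 | 0.80 | 18.7% | 2.00 | 56.2% |
| 7 days | 4 | 7 | 10 | 0.467 | 1.40 | 0.70 | 16.7% | 2.10 | 59.7% |
| 7 days | 5 | 7 | 10 | 0.560 | 1.12 | 0.56 | 14.3% | 2.24 | 64.5% |
| 5 weekdays | 3 | 5 | 8 | 0.560 | 1.12 | 0.56 | 14.3% | 2.24 | 64.5% |
| 5 weekdays | 4 | 5 | 8 | 0.700 | 0.70 | 0.35 | 11.7% | 2.45 | 71.2% |
| 5 weekdays | 5 | 5 | 8 | 0.933 | 0 | 0 | 10.0% | 2.80 | 80.9% |

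**4. Without the session model.** Setting e directly, with F = 2.8 and I = 0:

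| e | Null intensity rejected | Frequency margin | Power |
|---|---|---|---|
| 0.5 | 11% | 2.55 | 74% |
| 1.0 | 13% | 2.30 | 67% |
| 2.0 | 23% | 1.80 | 49% |

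**The case against.** **The gap may not exist.** Next to twice-daily and once-a-day schedules, *daily* can be read as once rather than twice a day. That reading is available, but B's days per week are then unstated, and the same sentence still needs correcting.

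**The size rests on a model the documents do not support.** Linearity credits once-daily therapy with up to 4/7 of the C − A effect (A = 3, B = 7, C = 10). If the second session on the same day is what works, which fits the distributed-practice rationale in Section 3.0, e is near zero. In a shorter stay B also has fewer extra sessions. This stands as a limit on the numbers. It does not touch the algebra, and a trial testing whether frequency matters should not have to assume that extra sessions do nothing.

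**The 2.8 is a margin difference in Section 12.0, not C − A.** If 2.8 is taken as the frequency margin under the schedules as written, its power stays at 80.9%. The bias then moves to the intensity side. With A = 3, B = 7, C = D = 10, the mean gap in sessions is (7 + 3)/2 = 5, k = 2.8/5 = 0.56, e = 4 × 0.56 = 2.24 and the intensity bias is 1.12 points, against 0.80 above. The power loss depends on this choice; the presence of bias does not.

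**The low row could coherently mean not twice daily, with usual care as a pragmatic control.** B − A is indeed a valid comparison of that arm with usual care. It is not the effect of intensity alone, which is what the aims and the pooled test claim.

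**Moving B changes Aims III and IV.** It does widen the schedule gap between B and the frequent arms. But D − B becomes F rather than F − e, and B − C becomes I − F rather than I + e − F, which is closer to what those aims describe.

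**Conclusion.** The concern holds and should be fixed before the pooled contrasts are relied on. It is certain that the written schedules for A and B differ, and that nothing in the plan reconciles them. Given equal arms, additive effects and a common schedule in C and D, the shifts of +e/2 in the intensity margin and −e/2 in the frequency margin are exact.

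The size in PASS points is unknown. Under the linear 7-day illustration, the intensity bias is 0.56 to 0.80 points if *daily* is seven days and 0 to 0.56 if it is five weekdays. It is zero if both arms receive five sessions a week, or if extra once-daily sessions have no effect. Until the schedules are aligned, a positive intensity result or a null frequency result could be produced by the schedules.

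**What to change.** **Preferred: put B on the usual-care schedule.** Once a day, three to five days a week, 20 to 50 minutes, with the same written rule as A for choosing the number of days (none is given now, so one must be added). N stays at 168, the usual-care control is kept, the intensity bias is removed by design, and the frequency margin returns to the full 2.80 points (80.9% power) in the illustration. The cost is a protocol amendment to one arm and fewer sessions for B: 2 to 4 fewer over seven days if *daily* is seven days, 0 to 2 if it is five weekdays. A three-to-five-day range does not guarantee equal delivery.

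**If enrolment has started, or the schedules must stay:** this route avoids mixing two B schedules.

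1. Do not describe (B + D) versus (A + C) as a test of intensity alone.
2. Describe B − A as intensity plus daily sessions versus usual care.
3. Report D − C, where schedules match, as a supporting estimate of intensity at high frequency. It compares 42 with 42, so its SE is 7.2 × √(2/42) = 1.57 against 1.11 for the margin, and power for 2.8 points at 10% is about 55% against 81%. It does not replace Aim II.

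**In either case,** record sessions and minutes delivered and report them by arm. Clarify what *daily* means, what C and D receive on the other two early days, and that the factor labelled duration is frequency.

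**Not advised: raising A to daily.** This drops the standard-of-care control. With *daily* as seven days and k as in the first table, the frequency effect becomes k(10 − 7), which is 1.20 points for k = 0.400 and 1.68 for k = 0.560, with power 29% to 45%.
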